8.3.3 CLASSIFICATION OF AN ADVERSE EVENT

8.3.3.4 Severity of Event

For AEs not included in the protocol defined grading system, the following guidelines will be used to describe severity.

Mild – Events require minimal or no treatment and do not interfere with the participant's daily activities.

Moderate – Events result in a low level of inconvenience or concern with the therapeutic measures. Moderate events may cause some interference with functioning.

Severe – Events interrupt a participant's usual daily activity and may require systemic drug therapy or other treatment. Severe events are usually potentially life-threatening or incapacitating. Of note, the term "severe" does not necessarily equate to "serious".

8.3.3.5 Relationship to Study Intervention

All AEs must have their relationship to study intervention assessed by the clinician who examines and evaluates the participant based on temporal relationship and his/her clinical judgment. The degree of certainty about causality will be graded using the categories below. In a clinical trial, the study product must always be suspect.

Definitely Related – There is clear evidence to suggest a causal relationship, and other possible contributing factors can be ruled out. The clinical event, including an abnormal laboratory test result, occurs in a plausible time relationship to study intervention administration and cannot be explained by concurrent disease or other drugs or chemicals. The response to withdrawal of the study intervention (dechallenge) should be clinically plausible. The event must be pharmacologically or phenomenologically definitive, with use of a satisfactory rechallenge procedure if necessary.

Probably Related – There is evidence to suggest a causal relationship, and the influence of other factors is unlikely. The clinical event, including an abnormal laboratory test result, occurs within a reasonable time after administration of the study intervention, is unlikely to be attributed to concurrent disease or other drugs or chemicals, and follows a clinically reasonable response on withdrawal.

Potentially Related – There is some evidence to suggest a causal relationship (e.g., the event occurred within a reasonable time after administration of the trial medication). However, other factors may have contributed to the event (e.g., the participant's clinical condition, other concomitant events). Although an AE may rate only as "possibly related" soon after discovery, it can be flagged as requiring more information and later be upgraded to "probably related" or "definitely related", as appropriate.

Unlikely to be related – A clinical event, including an abnormal laboratory test result, whose temporal relationship to study intervention administration makes a causal relationship improbable (e.g., the event did not occur within a reasonable time after administration of the study intervention) and in which other drugs or chemicals or underlying disease provides plausible explanations (e.g., the participant's clinical condition, other concomitant treatments).

Not Related – The AE is completely independent of study intervention administration, and/or evidence exists that the event is definitely related to another etiology. There must be an alternative, definitive etiology documented by the clinician.]

8.3.3.6 Expectedness

The study investigator will be responsible for determining whether an adverse event (AE) is expected or unexpected. An AE will be considered unexpected if the nature, severity, or frequency of the event is not consistent with the risk information previously described for the study intervention, such as that described in the medication package insert.

8.3.4 TIME PERIOD AND FREQUENCY FOR EVENT ASSESSMENT AND FOLLOW-UP

Participants will have assessments including phlebotomy for safety laboratory every 6 months including baseline, 6-months, 12-months, and 18-months visits. In addition, participants will have monthly calls for monitoring of adverse events between visits. The safety laboratory tests will include complete blood count, basic metabolic panel, hepatic panel, and vitamin B12 (cobalamin). Cobalamin testing will allow to assess whether participants develop cobalamin deficiency and anemia, which could be due to metformin, or contraindications to metformin use such as hepatic insufficiency and severe renal insufficiency.

At each study visit, the investigator will inquire about the occurrence of AE and SAEs since the last visit. All AEs and SAEs will be captured on the appropriate eCRF. All AEs and SAEs occurring while on study drug

will be documented appropriately regardless of relationship. All AEs and SAEs will be followed to adequate resolution.

Any medical condition that is present at the time that the participant is screened will be considered as baseline and not reported as an AE. However, if the study participant's condition deteriorates at any time during the study, it will be recorded on the appropriate eCRF (e.g., AE or SAE).

Changes in the severity of an AE or SAE will be documented to allow an assessment of the duration of the event at each level of severity to be performed. AEs and SAEs characterized as intermittent require documentation of onset and duration of each episode.

8.3.5 ADVERSE EVENT REPORTING

The site investigator is responsible for monitoring the safety of participants enrolled into the study. If an adverse event necessitates modification of study drug dosing, this will be captured on the Dose Change Log eCRF.

All AEs and SAEs occurring from the first day of study enrollment (the day of randomization) to 30 days post last day of study drug dosing will be captured in the AE and SAE eCRF. Unless exempted as described in section 8.3.2, all SAEs, whether or not deemed drug-related or expected, must be reported to the CCC by the investigator or qualified designee **within 24 hours** of first becoming aware of the event. The investigator or qualified designee will enter the required information regarding the SAE into the appropriate module of the eCRF, which will automatically result in distribution of the information to the site-monitoring group, the Safety Event Adjudication Committee, and EMD Serono.

Pregnancy and cancer are not always serious by regulatory definition; however, these events must be submitted to the sponsor within the same time period as an SAE via the EDC.

If the eCRF system is temporarily unavailable, the event, including the investigator-determined causality to study drug should be reported via the back-up paper SAE form to Safety Surveillance. Upon return of the availability of the electronic data capture (EDC) system, the SAE information must be entered onto the eCRF.

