7 DISCONTINUATION OF STUDY INTERVENTION AND WITHDRAWAL OF PARTICIPANT

7.1 DISCONTINUATION OF STUDY INTERVENTION

Discontinuation of IP does not mean discontinuation from the study, and remaining study procedures should be completed as indicated by the study protocol. If a clinically significant finding is identified (including, but not limited to changes from baseline) after enrollment, the investigator or qualified designee will determine if any change in participant management is needed. Any new clinically relevant finding will be reported.

If participants develop diabetes by HbA1c criteria (6.5% or higher), they will be referred to their physicians to decide about treatment for diabetes. This may lead to discontinuation of IP upon consultation with the study's safety officer at the DCC. However, participants will be invited to remain in the study and will be analyzed following intent to treat.

If the medication is not discontinued due to an SAE and the investigator believes that the participant could be re-challenged with the discontinued medication per standard clinical practice, then this may be attempted after discussion with the DSMB and approval by the Medical Monitor.

If the medication was discontinued due to an SAE, then there should not be an attempt to restart the medication.

Any discontinuation of study drug will be recorded on the Dose Change Log eCRF.

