8.3 ADVERSE EVENTS AND SERIOUS ADVERSE EVENTS

8.3.1 DEFINITION OF ADVERSE EVENTS (AE)

Adverse events

Adverse event (AE) means any untoward medical occurrence associated with the use of an intervention in humans, whether or not considered intervention related. An AE can therefore be any undesirable sign,

symptom or medical condition occurring after starting IP, even if the event is not considered to be related to the pharmaceutical product. An AE can arise with any use of the drug (e.g., off-label use, use in combination with another drug) and with any route of administration, formulation, or dose, including an overdose (21 CFR 312.32 (a)). Headache, dizziness, lightheadedness, and gastrointestinal upset are AEs that will be specifically questioned about during phone calls and study visits.

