9.4.4 SAFETY ANALYSES

The number of SAEs will be tabulated by type for the entire study sample as well as by treatment group. Any treatment group differences in SAEs enumerated for interim analyses will remain blinded to investigators associated with this study. Unmasked results will be made available only during the closed sessions of DSMB meetings.

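### The protocol gives conflicting rules on how long adverse events are captured after study drug stops; under the 30-day rule in 8.3.5, by-arm SAE counts could be truncated unequally

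*Protocol*

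**What the plan says.** The Protocol describes the capture period in several places.

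- **8.3.5:** events from the day of randomisation "to 30 days post last day of study drug dosing will be captured in the AE and SAE eCRF". This is the only place with both an explicit start and an explicit end.
- **8.3.4:** "All AEs and SAEs occurring while on study drug" are to be documented whatever their relationship to drug. The sentence just before it sets no limit: "All AEs and SAEs will be captured on the appropriate eCRF". The same section also has a pre-existing condition recorded "if the study participant's condition deteriorates at any time during the study".
- **8.3.6:** the clinician reports any SAE to the sponsor; no time limit is stated.
- **Table 7:** the adverse-event row is marked in every column from screening/baseline to month 18, and no footnote restricts it to participants on drug.
- **8.3.1:** the definition of an AE covers a "symptom or medical condition occurring after starting IP", so it starts at first dose and not at randomisation.

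Two further sections matter for the consequence. Section 7.1 states "Discontinuation of IP does not mean discontinuation from the study" and asks that the remaining procedures be completed. Section 9.4.4 states "The number of SAEs will be tabulated by type for the entire study sample as well as by treatment group", with no on-treatment restriction and no denominator for observation time.

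**The concern.** Two sites could each follow the protocol faithfully and record different events for a participant who stops drug and stays in follow-up. One would close the AE and SAE forms 30 days after the last dose under 8.3.5. The other would keep recording to month 18 under Table 7 and 8.3.4.

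Under the 8.3.5 rule, capture time depends on how long a person stays on drug, while the SAE table is by treatment group with no adjustment for that time. If stopping differs between arms, raw SAE counts could differ with no true difference in risk. The cut-off is also not neutral within an arm. When drug is stopped because of an SAE, 7.1 rules out restarting it, so that person's later SAEs would fall outside the window for good.

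The counts are used: the DSMB reviews safety at least twice a year (10.1.6), and the safety profile in subgroups can modify the phase III population (9.4.10).

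There is a smaller mismatch at the start. Section 8.1 allows up to 2 months between enrolment and titration for baseline MRI and PET. An event in that gap falls inside the 8.3.5 window but outside the 8.3.1 definition.

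**Working it through.** The plan states no figure on this point, so there is nothing to reproduce. The check compares the texts and then sizes the effect if 8.3.5 is applied.

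**Step 1. A participant who stops drug at month 2 and has an SAE at month 10**

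| Text | Is the month-10 SAE recorded? |
|---|---|
| 8.3.5 (last dose + 30 days) | No; the window closed at about month 3 |
| 8.3.4, on-drug sentence | Not covered |
| 8.3.4, general capture sentence | Yes |
| 8.3.6, any SAE | Yes, reported to the sponsor |
| Table 7 with 7.1 | Yes; AE collection is scheduled at every contact |

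The answers conflict and no text ranks them.

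**Step 2. Inputs for the size**

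- Participants per arm: 163 (synopsis).
- Follow-up: 18 months (synopsis).
- Stopping rate: 7.5% stopped metformin but stayed in the study (pilot results, 2.2.7; 3 of 40).
- Month of stopping, t: not given; month 2 assumed, with months 1, 3 and 9 as a range.
- Placebo stopping: not given; 0% to 5% assumed.
- Event rates: assumed constant over time and equal in the two arms.

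**Step 3. Person-time lost under 8.3.5**

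Share lost = p × (18 − t − 1) / 18, taking 30 days as one month.

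- p = 7.5%, t = 2: 0.075 × 163 × 15 = 183 person-months of 163 × 18 = 2,934, or 6.25%.
- t = 1: 0.075 × 16/18 = 6.7%.
- t = 3: 0.075 × 14/18 = 5.8%.
- t = 9: 0.075 × 8/18 = 3.3%.

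**Step 4. Effect on the by-arm count with no true difference**

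Count ratio = (1 − share lost, metformin) / (1 − share lost, placebo).

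- Metformin 7.5%, placebo 0%, t = 1: 0.933 / 1.000 = 0.93.
- Metformin 7.5%, placebo 5%, t = 9: 0.967 / 0.978 = 0.99.
- Equal stopping in both arms: 1.00.
- Metformin 2.5%, placebo 7.5%, t = 1: 0.978 / 0.933 = 1.05.

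The last two lines show that the sign depends entirely on which arm stops more.

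**Step 5. In events**

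With an assumed 0.15 SAEs per participant over 18 months, each arm expects 163 × 0.15 = 24.4. With 7.5% stopping metformin at month 1 and no placebo stopping, 24.4 × 0.933 = 22.8 are counted on metformin against 24.4 on placebo, a gap of 1.6. If the counts are Poisson, the standard deviation of the difference is about √(24.4 + 22.8) ≈ 7.

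**Step 6. After the fix**

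With capture to last study contact regardless of dosing, the share lost by this route is 0% in both arms.

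**The case against.** The strongest reply is that the protocol, read as a whole, already captures these events. The general sentence in 8.3.4, the SAE duty in 8.3.6 and the AE row of Table 7 carry no dosing condition, and 7.1 keeps people who stop drug on that schedule. Section 8.3.1 is a definition and not a collection period, and the on-drug sentence in 8.3.4 can be read as a rule about causality. A window of last dose plus 30 days can also be a legitimate on-treatment choice. Much of this stands. The under-count is conditional on sites applying 8.3.5, which is not the widest text, and 8.3.1 should not be counted as a rival window. It does not remove the conflict, because 8.3.5 is the only text that gives the AE and SAE eCRF an explicit start and stop, so sites may reasonably follow it.

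A reader might go further and infer that SAEs will be under-counted on metformin, biasing the comparison in its favour. The documents do not support that. Gastrointestinal intolerance makes more stopping on metformin plausible, but no placebo rate is given. The 7.5% comes from a short-acting product titrated weekly, whereas this trial uses an extended-release form chosen for better tolerability. Stopping after a diabetes diagnosis could also be commoner on placebo. Nor can one infer that later deaths and hospitalisations would go wholly unrecorded: 7.3 has the site enter the last contact date, including for death, in the eCRF, and 8.3.6 covers any SAE.

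Finally, 9.4.4 plans a tabulation with no test, and the illustrated gap of 1.6 events is small beside chance variation of about 7.

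**Conclusion.** The contradiction is established from the text. Section 8.3.5 and the on-drug sentence in 8.3.4 cannot be reconciled with the rest of 8.3.4, with 8.3.6, or with Table 7 and 7.1. Distortion of the by-arm SAE counts is a possible consequence, conditional on sites applying 8.3.5 and on stopping that differs between arms. Its direction is open.

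At the pilot's metformin stopping rate the effect is modest: about 6% of that arm's person-time with stopping at an assumed month 2, and 3% to 7% over months 1 to 9. The SAE count ratio is 0.93 to 0.99 if placebo stopping is 0% to 5%. These figures assume constant, equal event rates and otherwise complete follow-up. The loss scales in proportion to the stopping rate, but the protocol offers no basis for a rate above 7.5%.

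The point still merits correction: it concerns what is recorded, and events not recorded prospectively may be hard to recover at the analysis stage.

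**What to change.** Reconcile 8.3.4, 8.3.5, 8.3.6 and Table 7 to a single capture window: all AEs and SAEs from randomisation to the last study contact, for everyone in follow-up, whatever their dosing status. Align the start point in 8.3.1 with it, so that events between randomisation and first dose are treated the same way throughout.

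If an on-treatment summary is wanted, derive it from dosing dates (first dose to last dose plus 30 days) and do not restrict what sites record. Dose changes and discontinuations already go on the Dose Change Log. How the two summaries are presented can be left to the statistical analysis plan.

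The cost is protocol wording, eCRF guidance and some additional AE and SAE forms. Visits and monthly contacts are already scheduled to month 18, so no new contact is needed.

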8.3.6 SERIOUS ADVERSE EVENT REPORTING

The study clinician will immediately report to the sponsor any SAE, whether or not considered study intervention related, including those listed in the protocol or investigator brochure and must include an assessment of whether there is a reasonable possibility that the study intervention caused the event. Study endpoints that are serious adverse events (e.g., all-cause mortality) must be reported in accordance with the protocol unless there is evidence suggesting a causal relationship between the study intervention and the event (e.g., death from anaphylaxis). In that case, the investigator must immediately report the event to the sponsor.

All SAEs will be followed until satisfactory resolution or until the site investigator deems the event to be chronic or the participant is stable. Other supporting documentation of the event may be requested by the DCC/study sponsor and should be provided as soon as possible.

The study sponsor will be responsible for notifying the FDA, IRB and DSMB of any suspected, (possibly, probably, definitely related) unexpected serious adverse reaction (SUSAR) as soon as possible, but in no case later than **7 calendar days** after the sponsor's initial receipt of the information. In addition, the sponsor must notify FDA and all participating investigators in an investigational new drug (IND) safety

report of potential serious risks, from clinical trials or any other source, as soon as possible, but in no case later than **15 calendar days** after the sponsor determines that the information qualifies for reporting.

8.3.7 REPORTING EVENTS TO PARTICIPANTS

We anticipate the following types of reports of events to participants:

- Reporting of results of safety laboratory tests: All participants will receive written full reports of the complete blood count, basic metabolic panel, hepatic panel, and cobalamin level. These reports will indicate the normal levels for each value and will encourage participants to call the site PIs with any questions and/or consult with their primary care physicians. If abnormalities in these laboratory tests are deemed to be due to the study intervention, or constitute a new contraindication to the study intervention, participants will be informed by the site PI by telephone, and in writing.
- Reporting of incidental findings in brain MRI. As indicated in section 2.3.3, there are 4 levels of incidental findings on MRI; level 3 requires non-urgent follow-up, and level 4 requires emergency follow-up. Site PIs will receive neuroradiology safety reads of the MRI within 72 hours. If level 3 findings are reported, the site PI will contact the participants via telephone, and with the permission of the participant, their medical provider, in order to inform of the incidental finding. In addition, a written report of the incidental finding will be mailed to the participant and medical provider. For level 4 incidental findings, the participant will be contacted on an urgent basis with the instruction to present to an emergency room or urgent care provider immediately.
- Reporting of new adverse events in our study, other studies, or the medical literature. In consultation with the DSMB and SIRB, we will compose a letter explaining the appearance of new information on the study drug reported in medical journals, other studies, and our study. This information will also be added to the consent form and participants will be re-consented at the next available visit.

8.3.8 EVENTS REQUIRING A CHANGE IN IP DOSING

At each study visit, the investigator will inquire about the occurrence of events that require a change in IP dosing, which may include, but are not limited to, hospitalizations, surgeries, and procedures that require holding metformin. Clinical events such as the development of anemia and/or B12 deficiency, and the development of contraindications to metformin, such as New York Heart Association Class III or IV congestive heart failure, and renal or hepatic insufficiency deemed to be of clinical significance are other examples of events that may require a change in IP dosing. Changes in IP dosing, and the associated reason, will be captured on relevant eCRF pages. Events above pre-specified thresholds as outlined in the Data Safety Monitoring Plan will trigger a review by the DSMB to investigate the presumed cause and impact of these events. Such events are initially reviewed by a Data Coordinating Center (DCC) staff member to determine if an event threshold has been reached, at which time the study investigators and the DSMB will be notified.

8.3.9 REPORTING OF PREGNANCY

Although our cohort will be between the ages of 55 and 90 years, there is the possibility of pregnancy. If, following initiation of the IP, it is subsequently discovered that a study participant is pregnant or may have been pregnant at the time of IP exposure, the IP will be permanently discontinued.

The Investigator must immediately notify the PI and the Safety Event Adjudication Committee of this event within 24 hours and in accordance with SAE reporting procedures.

Follow-up information regarding the course of the pregnancy, including perinatal and neonatal outcome must be reported. Any associated AEs or SAEs that occur to the mother or fetus/child will be recorded in the SAE CRFs.

Protocol-required procedures for study discontinuation and follow-up must be performed on the participant unless contraindicated by pregnancy.

8.4 UNANTICIPATED PROBLEMS

8.4.1 DEFINITION OF UNANTICIPATED PROBLEMS (UP)

The Office for Human Research Protections (OHRP) considers unanticipated problems involving risks to participants or others to include, in general, any incident, experience, or outcome that meets all of the following criteria:

- Unexpected in terms of nature, severity, or frequency given (a) the research procedures that are described in the protocol-related documents, such as the single IRB (sIRB)-approved research protocol and informed consent document; and (b) the characteristics of the participant population being studied;
- Related or possibly related to participation in the research (“possibly related” means there is a reasonable possibility that the incident, experience, or outcome may have been caused by the procedures involved in the research); and
- Suggests that the research places participants or others at a greater risk of harm (including physical, psychological, economic, or social harm) than was previously known or recognized.

